Healthy male and female volunteers will be recruited and informed that they may be eligible to participate in a study that examines the role of endogenous opioids in processing several types of touch. We will explain that participants will receive saline and naloxone on two different days with a minimum 24 hour wash-out period between testing sessions to minimize the possibility of carry-over effects, serum half-life for naloxone ranges from 30 to 81 minutes. The drugs will be administered in association with different types of touch stimuli on the calf of the leg including light brush stroking of the skin, compression around the limb, and application of heat to the skin, including moderately painful heat. Functional magnetic resonance imaging (fMRI) will be conducted simultaneously to observe the effect of the drug infusions on touch processing. The

purpose of the study is to identify the role of endogenous opioids in perception of light and deep pressure touch as well as experimental pain.

A pre-screening telephone call will be conducted to determine eligibility. If eligibility requirements are met, subjects will be scheduled for the test sessions. Screening will be accomplished under NCCIH protocol 16-AT-0077 (“Clinical and Scientific Assessment of Pain and Painful Disorders”). If deemed eligible, the participant will provide consent for the current protocol prior to performing any procedures specific to this protocol. Consent may occur during an additional, separate visit from the subsequent two research sessions. See Figure 1 for Study Flow. All visits will be on an outpatient basis and all experiments will be conducted in Building 10 of the NIH.

All subjects will be informed about naloxone, including its pharmacological properties, clinical use, and possible side effects. Subjects will also be informed that they may withdraw from participation at any time during the course of the study and that they will be compensated for each portion of the study that they have completed.

[figure not shown]

Figure 1. Study Flow. Each MRI session will follow the timeline shown.

b. Recruitment

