Consent will be obtained before any study procedures will be done. Upon arrival at the Clinical Center, the participant will be assigned a CRIS identification number through the NIH Admissions Office. The consent form will be explained and all questions will be answered before the participant is asked to sign the consent form (see Section 14 for details). Consent may occur during an additional, separate visit from the subsequent two research sessions.

Participants eligible to proceed will be asked to undergo two testing sessions, separated by at least 1 day, in the NIH Clinical Research Center's Functional MRI Facility (FMRIF, Building 10, Room B1D307 or B1D305). Each participant will receive naloxone on one day, and saline on the other, with drug order counterbalanced across subjects. At each visit, a urine sample will be collected from all participants for drug screening. In addition, at each visit, participants who are able to become pregnant will also take a urine pregnancy test. Date of onset for previous menstrual cycle will be documented to allow for later analysis of confounds of menstrual cycle in perceptual outcomes. Medical inclusion and exclusion criteria will be reviewed with the participant at the beginning of each study session to confirm continued eligibility. The participants will have their intravenous line placed before any part of the fMRI will start. A baseline scan including data collection for all sensory conditions will be collected before the intravenous infusion. Drug infusion will then start with a bolus injection followed by a continuous infusion of naloxone or saline and the full sensory paradigm will be repeated. An anatomical MRI will also be acquired.

Sensory testing paradigm

Sensory testing will occur on the participant's left lower leg. While it is most common for brushing paradigms to brush on the hairy skin on the arm (C-LTMR fibers primarily innervate

hairy skin), several studies have reported the same preference for slow, C-LTMR brushing on the leg [35], including the shin [36]. According to our unpublished data the calf is also a site of high pleasantness ratings for deep compression, and more accessible in the MRI scanner. We will therefore conduct all sensory testing on subjects' lower leg. Participants will be asked to wear shorts or change into scrubs for each session in order to access the lower leg.

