We have included a number of validated questionnaires to assess variations across individuals. Some of these items include sensitive questions about one's psychological and emotional state. Participants will be informed that they can skip any questions they do not wish to answer, and that participation is voluntary.

8. Subject Safety Monitoring

Participants will be monitored by the study investigators during all study visits for study outcomes and adverse events. All subjects will be instructed about, and receive practice with, each test before they begin to perform it and, before a test is formally administered, adequate comprehension of the instructions for each test will be insured by the test examiner.

During an assessment, testers are usually in the room with the subject or in the room just outside the fMRI room. Study staff will monitor individuals during participation and subjects will be encouraged to tell experimenters of any discomfort. If apparatus, etc., cannot be adjusted to relieve discomfort, the experiment will be stopped. Subjects may withdraw at any time.

During MRI scanning, subjects will be given a call button and instructed to use it in case of emergency or if the subject feels any discomfort in the scanner. Throughout the scan session, verbal contact with the subject will be maintained from the control room via an intercom device.

Participants can withdraw from this study at any time and for any reason without loss of benefits or privileges to which they are otherwise entitled or prohibition from enrolling in other clinical protocols. Investigators can remove a participant from the study if an exclusionary condition develops, if the investigator believes that continuation is not in the best medical interest of the subject, or if the subject is unable to comply with study requirements. Sessions

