may also be terminated early due to factors that do not directly influence subject safety, such as technical difficulties (e.g. equipment malfunction, computer issues), if schedule conflicts arise (e.g. participant arrives late or needs to leave early; MRI scanner availability is not sufficient to complete the experiment; delays in Clinical Center waiting time, time to process lab orders and lab results). When sessions are terminated early, participants may be asked whether they wish to reschedule. If participants end a session due to discomfort, they will be asked whether they want to continue with other phases of the study, and/or participate in other sub-studies in the protocol.

A. Withdrawal Criteria

Participants can withdraw from this study at any time and for any reason without loss of benefits or privileges to which they are otherwise entitled, or prohibition from enrolling in other clinical protocols. Investigators can remove a participant from the study if an exclusionary condition develops, if the investigator believes that continuation is not in the best medical interest of the subject, or if the subject unable to comply with study requirements.

B. Criteria for Stopping study

In all subjects, procedures will be stopped if requested by participants or if the investigators feel it is in the best interest of the participant.

9. Outcome Measures

a. Primary outcome measures

The primary outcome is the change or difference in pleasantness rating between post-drug and pre-drug of light stroking.

b. Secondary outcome measures

The secondary outcomes include change or differences between post-drug and pre-drug ratings for 1) pleasantness and/or intensity of deep pressure 2) unpleasantness and/or intensity of cutaneous heat pain.)

c. Tertiary outcome measures

- 1) Determine the role of mood or anxiety changes in mediating the effect of endogenous opioids on these perceptual measures; 2) Determine changes in the brain activation related to these effects.

10. Statistical Analysis

a. Analysis of data/ study outcomes

Testing for normal distribution

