All data will be assessed for normality of distribution using the Shapiro Wilk W test. A significant W statistic indicates that the hypothesis of a normal distribution should be rejected, i.e. a significant W indicates skewed data. If the data is skewed the data transformation method will be chosen based on the distribution (Box-Cox method) of the dependent variable. The resulting transformed data will be analyzed with parametric statistics. In the descriptions below we will describe the parametric statistical tests. If data transformation does not work, non-parametric tests will be applied.

Behavioral Data

All behavioral data will be analyzed using SPSS or similar statistical package. A significance level of $p < 0.05$ will be adopted for all analyses.

For the primary and secondary outcomes, we will use paired t-test to evaluate the drug effect. To determine whether the effect of drug on touch pleasantness is mediated by mood, we will use Wager & Lindquist's Multilevel Mediation and Moderation (M3) Toolbox. In the analysis, the dependent variables are the sensory ratings, the independent variable is the drug and the mediator variable is mood.

MRI data will be analyzed using standard brain imaging packages such as FSL or AFNI. For the initial analysis, the individual performing the analysis will be blinded. Whole brain analysis will be the first analysis performed followed by analysis looking at individual activations (parameter

estimates) in regions of interest including the insula, cingulate cortex and orbitofrontal cortex. These activations will be used to conduct a mediation analysis of these brain areas in mediating the effect of drug on touch pleasantness ratings. In this analysis, the dependent variables are the perceptual ratings, the independent variable is the level of stimulus and the mediator is the BOLD activation in the brain area of interest (ROI).

b. Power analysis

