In order to yield meaningful statistical analyses of the psychophysical data, and specifically for our primary outcome measure, we estimate that the sample size required to complete the study would be 24 healthy participants. G*Power (<http://www.gpower.hhu.de>) was used to compute the necessary sample size. We used a Cohen's effect size $d = 0.61$ based on the means and standard deviations of pleasantness rating changes in our previous study of naloxone versus saline [9], statistical power of 80%, and Type I error probability $\alpha=0.05$. The effect size of 0.61 is clinically important for the pleasantness rating outcome. We expect a 20% dropout rate of participants based on prior NIH studies. Thus, we will enroll up to 30 participants and dropouts will be replaced.

11. Human Subjects Protection

a. Subject selection

Accrual will be equitable among the participants eligible for this study.

b. Justification for exclusion of children

The current study constitutes initial research into the affective mechanisms of light stroking and deep pressure touch and involves procedures such as intravenous drug infusion that are likely to not be well tolerated by children, with no particular benefit to them. In addition, there is evidence that affective touch perception differs by age, both in perception and in brain processing, with children and older adults differing from young and middle-aged adults [47, 48] which would add significant variability to the data. A separate, age-specific study in children is thus warranted and preferable and children will not be included in the current study.

c. Justification for exclusion of other vulnerable subjects

Participants who do not speak English will not be enrolled because our complete set of questionnaires is only validated in English.

Individuals without consent capacity will be excluded because the research question can be answered by enrolling only adults who can consent, and participation does not offer the potential for important clinical benefit. Therefore, the risk outweighs the benefit in this population.

Pregnant women and lactating women are excluded because pregnancy and lactation significantly alter a women's hormonal profile and hormones affect touch processing [49, 50], and because MRI is contraindicated for pregnancy.

Individuals weighing more than 550 lbs. will be excluded because of the weight limit of the MRI scanner.

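### The paired t-test on change is valid and meets its stated power; adding the recorded drug order to the model would be a cheap gain in robustness, and the session baseline is an optional extra

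*Combined protocol and SAP*

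**What the plan says.** Section 10a (Behavioral Data) gives the whole primary and secondary comparison in one sentence: "For the primary and secondary outcomes, we will use paired t-test to evaluate the drug effect". Section 9a defines the endpoint: "The primary outcome is the change or difference in pleasantness rating between post-drug and pre-drug of light stroking". Section 9b does the same for the other ratings: "The secondary outcomes include change or differences between post-drug and pre-drug ratings". Read with Hypothesis 1 in section 2, the test compares each participant's change under naloxone with the same participant's change under saline.

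Section 4d supplies two further pieces of information. Each participant has both drugs "with drug order counterbalanced across subjects", so order is known for everyone. And "A baseline scan including data collection for all sensory conditions will be collected before the intravenous infusion", so each session has its own pre-drug rating. Order is not mentioned in section 10a.

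The plan already limits session effects. Section 8 provides that "All subjects will be instructed about, and receive practice with, each test before they begin to perform it", and section 4a separates the sessions "with a minimum 24 hour wash-out period between testing sessions to minimize the possibility of carry-over effects". Sections 3a and 10b replace dropouts but do not say which drug order a replacement receives. Section 10b takes d = 0.61 "based on the means and standard deviations of pleasantness rating changes in our previous study of naloxone versus saline".

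**The concern.** Subtracting the same-session baseline removes any session shift that affects pre-drug and post-drug ratings alike. It does not remove a difference between sessions in how far ratings move within a session. An example would be more habituation to brushing during the first scan than during the second. Call that difference π: session 1 minus session 2, not due to drug.

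If π is not zero, the paired t-test treats it as noise when the two orders have equal numbers, because participants with opposite orders carry it with opposite signs. When completers are unequal by order, part of π enters the estimated drug effect. A term for order removes both consequences and needs no new data. At stake are some power and a small possible bias in the primary estimate.

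**Working it through.** **Inputs from the documents.** d = 0.61, 80% power, α = 0.05, 24 completers, 30 enrolled (section 10b). Sidedness is not stated; two-sided reproduces the plan.

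**Inputs assumed.** π, in SDs of the paired difference, at 0.1, 0.25 and 0.5. r is the correlation of the naloxone-minus-saline differences in pre-drug and post-drug ratings. k is the post-drug SD divided by the pre-drug SD of those differences.

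**1. The plan's own figure.** Paired t-test, noncentrality d√n, df n−1. At n = 24: 0.61 × √24 = 2.99, df 23, power 81.6%. At n = 23: 79.8%. So n = 24 is reproduced, and 24/(1 − 0.20) = 30.

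**2. Model.** For each participant, D = (change under naloxone) − (change under saline) = d + π·s + e, with s = +1 for naloxone first and −1 for saline first. Let n1 be the number with naloxone first.
- The paired t-test estimates mean(D) = d + π(n1 − n2)/N.
- Regression of D on s estimates d by its intercept, which is the average of the two order-specific means. It is free of π, with SE = SD(e) × √((1/n1 + 1/n2)/4) and df N − 2.

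**3. Cost of the sequence term if π = 0.** Its power is 81.5% at 12/12, 81.2% at 13/11 and 80.4% at 14/10, against 81.6% for the paired test. The cost at 12/12 is 0.8164 − 0.8148, about 0.2 point. At 13/11 it is 0.4 and at 14/10 it is 1.2 points.

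**4. Power at 12/12 if π exists.** Section 10b does not say whether the SD behind d = 0.61 includes session variation, so both readings are shown. Reading A sets SD(e) = 1. Reading B sets SD(e) = √(1 − π²).

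| π | A: paired t | A: sequence term | B: paired t | B: sequence term |
|---|---|---|---|---|
| 0.1 | 81.4% | 81.5% | about 82% | about 82% |
| 0.25 | 79.9% | 81.5% | about 82% | about 84% |
| 0.5 | 74.4% | 81.5% | about 85% | about 91% |

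The two tests break even at π of about 0.07 under both readings; below that the paired test is very slightly ahead. Under A the paired test falls to 80% at π = 0.24. Under B it never falls below target at 12/12.

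**5. Unequal completers.** The bias of the paired test is π × 2/24 at 13/11 and π × 4/24 at 14/10. For π = 0.1, 0.25 and 0.5:
- 13/11: 0.01, 0.02 and 0.04 SD.
- 14/10: 0.02, 0.04 and 0.08 SD, or 3%, 7% and 14% of d, in either direction.

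Paired-t power at 14/10 under A, when the bias adds to or takes from the drug effect, is 83/79%, 85/74% and 85/61%. The sequence term gives 80.4% throughout, without bias.

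**6. Type I error of the paired t-test (reading A).** For π = 0.1, 0.25 and 0.5 it is 4.9, 4.4 and 2.9% at 12/12, and 5.0, 4.8 and 4.2% at 14/10. It is not inflated. Only at 15/9 did simulation show an excess, at most about 6.2% for π up to 1 SD.

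**7. Adding the baseline difference.** Relative to the change score, the residual variance ratio is k²(1 − r²)/(1 + k² − 2rk). At k = 1, r = 0.5 it is 0.75/1 = 0.75. At k = 1.4, r = 0.7 it is 0.9996/1.00 = 1.00, so there is no gain to set against the lost degrees of freedom. Simulated power with sequence and baseline at 12/12, π = 0 (40,000 trials per cell), against 81.6%:

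| k | r = 0.3 | 0.5 | 0.7 | 0.8 | 0.9 |
|---|---|---|---|---|---|
| 1.0 | 93.1% | 89.5% | 85.2% | 83.5% | 81.4% |
| 1.2 | 88.9% | 84.6% | 81.1% | 79.4% | 80.4% |
| 1.4 | 86.0% | 81.6% | 79.3% | 80.0% | 85.6% |

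Eight cells gain, one ties and six lose. Two fall just under the 80% target.

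**The case against.** The strongest case is that nothing here is wrong. A paired t-test on same-session change with counterbalanced order is a standard crossover analysis, and it reaches the plan's target. π is hypothetical: subtraction already removes ordinary session shifts, participants practise each test, and section 4c requires a clinical MRI and sensory testing at screening, so session 1 is not a first exposure. A π of 0.5 would be 0.5/0.61 = 82% of the drug effect. Under reading B there is no shortfall at 12/12. The normality steps in section 10a were also written with simple tests in mind. All of this stands, and it keeps the point minor. It does not make the sequence term unsound, because the cost is small and the protection does not depend on knowing π.

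A reader might go further in four ways that the documents or the figures do not support:
- That the paired test is invalid or inflates type I error. It does not at 12/12 or 14/10.
- That a sequence term gains power whenever π exists. At 12/12 it does so only above about 0.07 SD.
- That the baseline covariate can be relied on to add power. Six of 15 assumed cells lose.
- That silence on replacement order shows balance will be lost. It shows only that the plan does not say.

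Carry-over is not the issue either: with a half-life of at most 81 minutes, 24 hours is at least 1440/81, about 18 half-lives.

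**Conclusion.** The planned test is valid near balance and delivers 81.6% power on the plan's own d, taken as the mean paired difference over its SD. Leaving drug order out forgoes a cheap safeguard. At 12/12 the sequence term gives up about 0.2 point if π = 0; under reading A it recovers 1.6 points at π = 0.25 and 7.1 points at π = 0.5. At unequal splits it removes a bias of up to 0.08 SD (14/10, π = 0.5). The case for the baseline covariate is weaker, since its effect runs from about +11 to −2 points depending on r and k. It helps most when r is low and k is near 1.

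π, r and k are assumptions, because the documents give none of them. The point is a minor improvement in efficiency and robustness, held with medium confidence.

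**What to change.** In section 10a, define the primary test as the t-test of the intercept in a regression of the naloxone-minus-saline difference in change on sequence, coded +1 for naloxone first and −1 for saline first. Keep the paired t-test as a sensitivity analysis. The endpoint in section 9a is unchanged. Use the same model for the secondary ratings.

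State that the normality check applies to the model residuals. If a non-parametric fallback is needed, a rank-sum comparison of the session-1-minus-session-2 difference in change between the two orders is the matching test.

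The naloxone-minus-saline difference in pre-drug rating may be added as a second covariate, decided in advance and with its possible loss stated. With that covariate in the model, using the post-drug difference or the change difference as response gives the same intercept, standard error and p-value: P = a + b·s + c·B implies P − B = a + b·s + (c − 1)·B.

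Add one sentence giving each replacement the drug order of the participant replaced, handled so that the blind is kept.

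The cost is a few sentences, one error degree of freedom (two with baseline), the 0.2 to 1.2 points of power shown above if π = 0, and a note in section 10b that the sample size was computed for the paired t-test. No new data are needed.

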Protocol Title: Sensory and Opioid Mechanisms of Affective Touch

Abbreviated Title: Affective Touch

Protocol Number: 17-AT-0075

Date of This Submission/Version: 07/27/2020, Version 1.7

Principal Investigator

M. [name]	NCCIH	[name]	[contact]	[contact]
----------------------------	-------	---------------------	--------------	-----------------------

Human Research Protections Program Investigator and Staff Training:

For this protocol, the following "Just in time" human subjects protection training courses are required for investigators and staff:

None

Total requested accrual

30 Healthy Volunteers

Project Uses Ionizing Radiation: No Yes

IND/IDE No Yes

Durable Power of Attorney No Yes

Multi-institutional Project No Yes

Data and Safety Monitoring Board No Yes

Technology Transfer Agreement No Yes

Samples are being stored No Yes

Flesch-Kincaid reading level of consent form: 8.3

Précis:

Objective: Our recent pilot study found evidence suggesting that blocking endogenous opioid release increases the pleasantness associated with having the skin stroked. Deep pressure touch (observed in hugs and massage) also typically conveys a sense of pleasantness. This increased pleasantness contrasts with evidence that blocking endogenous opioid release increases pain. The current study will examine the role of endogenous opioids in the pleasantness of light skin stroking and deep pressure touch, and contrast it with their role in the unpleasantness of a painful heat stimulus. Further, it will examine the neural basis of observed perceptual changes, using fMRI. This study constitutes the first study of the K99 phase of a K99/R00 grant application recently submitted to NCCIH by [name].

Study Population: 30 healthy participants will be enrolled in the study.

Design: Participants will receive intravenous saline or intravenous naloxone on separate days to investigate the effect of mu-opioid antagonism on the intensity and pleasantness of superficial and deep affective touch and the intensity and unpleasantness of cutaneous heat pain. Using a double-blind cross-over design, functional Magnetic Resonance Imaging (fMRI) will be conducted during sensory testing before and after the infusion of each drug to examine the neural mediation of opioid effects on touch perception. Ratings of mood, anxiety, pain intensity, pleasantness/unpleasantness, wanting and liking will also be collected throughout the study session.

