receptors on pain perception have produced conflicting results: no effect on pain [21-24], increased pain following high dose and decreased pain at low dose naloxone[25-28]. The same contradictory findings are true for several rodent studies [29-32]. To our knowledge, the ratings in the human studies were all unitary measures of pain intensity. However, a more recent study on this topic [33] utilized rating systems for both pain unpleasantness and pain intensity allowing the authors to differentiate the affective component of pain. The opioid blockade significantly increased pain unpleasantness ratings of experimental pain but the pain intensity ratings remained unaffected [33]. Our aim is to replicate this finding and add to it brain imaging data (fMRI) to characterize the brain areas associated with producing this dichotomized pain perception. By deciphering this neuronal process we could potentially also understand how mood can alter pain unpleasantness independent of pain intensity [34], if understood these components strengthen therapeutic strategies for treatment of chronic pain using mood altering therapies.

2. Study Objectives

Hypothesis 1 (primary outcome): Participants will experience a significant increase in the pleasantness but not intensity of cutaneous brushing and deep skin/muscle pressure after administration of naloxone (compared to saline).

Hypothesis 2 (secondary outcome): Participants will experience a significant increase in the unpleasantness but not intensity of cutaneous heat pain after naloxone administration.

Hypothesis 3 (secondary outcome): The effect of endogenous opioids on perception will be partially mediated by changes in mood, with negative mood increasing the pleasantness of pleasant touch and increasing the unpleasantness of pain.

Hypothesis 4 (secondary outcome): Stimulus-evoked neural activations will be modulated by naloxone administration, with preferential effects in cingulate cortex and insula.

3. Subjects

a. Description of study populations

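### The ROI mediation analysis is meant to explain the drug effect, but its stated model contains no drug term

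*Combined protocol and SAP*

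**What the plan says.** Two consecutive sentences in the MRI paragraph of Section 10a matter here. The first gives the purpose: ROI activations will be used to "conduct a mediation analysis of these brain areas in mediating the effect of drug on touch pleasantness ratings". The second describes that same analysis. It takes perceptual ratings as the dependent variable and states that "the independent variable is the level of stimulus and the mediator is the BOLD activation in the brain area of interest (ROI".

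Other places in the document bear on the intent:

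- The mood mediation, earlier in Section 10a, is set up differently: "the independent variable is the drug and the mediator variable is mood".
- The Précis (Design) says the fMRI is there "to examine the neural mediation of opioid effects on touch perception".
- Hypothesis 4 in Section 2 reads "Stimulus-evoked neural activations will be modulated by naloxone administration, with preferential effects in cingulate cortex and insula".
- The second tertiary outcome in Section 9c is "Determine changes in the brain activation related to these effects".
- Section 4d gives the layout. "Each participant will receive naloxone on one day, and saline on the other". "A baseline scan including data collection for all sensory conditions will be collected before the intravenous infusion", and the whole sensory paradigm is repeated once the infusion has begun.

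**The concern.** Mediation of a drug effect is the product of two paths, drug to mediator and mediator to outcome. The first path cannot be estimated in a model that leaves drug out. The aim and the model in Section 10a therefore describe different analyses.

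The error can run both ways. If stimulus level drives the ROI and the ROI drives ratings, the stated model can be positive although naloxone does nothing to BOLD. If naloxone acts through an ROI that does not distinguish the stimulus levels, the model can show nothing although drug mediation is real. An analyst who follows the plan could report a stimulus-coding result as evidence about an opioid pathway. An analyst who departs from it has no prespecified model to fall back on.

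**Working it through.** **The plan's own figures.** None is given for the mediation analysis. The only design calculation is for the primary outcome (Section 10b), and it reproduces: a two-sided paired t-test with d = 0.61 and α = 0.05 needs 24 participants (power 81.6%), and 24 / (1 − 0.20) = 30. This point does not affect it.

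**The two sentences side by side**

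| Element | Purpose sentence | Model sentence | Mood mediation |
|---|---|---|---|
| Effect to be explained | drug on touch pleasantness | – | drug on touch pleasantness |
| Independent variable | drug (implied) | level of stimulus | drug |
| Mediator | ROI activation | ROI BOLD | mood |
| Outcome | pleasantness ratings | perceptual ratings | sensory ratings |

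**Can stimulus level stand in for drug?** The term is not defined. The natural reading is the pairs in the sensory testing paradigm of Section 4d: slow/fast brushing, low/high pressure, low/high heat. That reading is an inference. Every one of these conditions is run in both sessions, before and during infusion. Level is therefore crossed with drug and carries no information about which drug was given.

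**Size, by illustration.** The textual mismatch is the proof. Every input below is assumed, because the documents give none: 24 subjects, 2 levels × 2 drugs coded 0/1, subject-centred data, residual SD 0.8.

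- BOLD = 0.6·level + d·drug + g·level·drug + error
- rating = 0.6·BOLD + k·drug + error
- True drug-mediated effect, averaged over levels = 0.6·(d + g/2)
- Expected value of the stated model = (0.6 + g/2) × slope of rating on BOLD given level
- That slope is 0.6 when k = 0. When g = 0 it is 0.6 + k·0.25d / (0.25d² + 0.473), where 0.473 = 0.8² × 71/96 (96 observations less 24 subject means and one level term).

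| Setting | True drug mediation | Stated model returns |
|---|---|---|
| g = 0, k = 0; d = 0, 0.2, 0.4, 0.6, 1.0 | 0, 0.12, 0.24, 0.36, 0.60 | 0.36 in all five |
| g = 0.6, k = 0; d = −0.6, −0.3, 0, 0.6 | −0.18, 0, 0.18, 0.54 | 0.54 in all four |
| g = 0, k = +0.5; d from 0 to 1.0 | 0 to 0.60 | 0.36 rising to 0.46 |
| g = 0, k = −0.5; d from 0 to 1.0 | 0 to 0.60 | 0.36 falling to 0.26 |
| level-to-BOLD path set to 0; d = 0.6, g = 0, k = 0 | 0.36 | 0.00 |

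Worked case, fourth row at d = 1.0: slope = 0.6 − 0.125/0.723 = 0.427, and 0.6 × 0.427 = 0.26. The simulation agrees with the formulas. The stated model's value can move with drug, in either direction, but in none of these families of settings does it track drug mediation.

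**Does a drug-based model recover the truth?** Take one stimulus type, with drug as independent variable and post-minus-pre BOLD and rating as mediator and outcome. For d = 0, 0.2, 0.4, 0.6 and 1.0 the mean estimate is 0, 0.12, 0.24, 0.36 and 0.60 to within 0.01, with k = 0 and with k = 0.5.

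**The case against.** The strongest reply is that this is a drafting slip. The purpose sentence, the Précis and the mood model all point to drug as the independent variable, so a sensible analyst would recover the intent. That is probably right about intent. But the model sentence is the only specification of this analysis, and as it stands it is wrong rather than merely incomplete.

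A second reply is that drug was meant as a moderator. The toolbox named for the mood analysis covers moderation, and Hypothesis 4 speaks of naloxone modulating stimulus-evoked activation. This is plausible, but the toolbox is named only for mood and no moderator is stated for the ROI model. Moderated mediation would also answer a different question from the one the purpose sentence sets.

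Third, the consequences are narrow. That stands. The ROI mediation is a design aim in the Précis but not a numbered hypothesis or listed outcome. Hypothesis 4 and the tertiary outcome concern changes in activation, which a plain drug contrast can address.

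Fourth, the repair brings limits of its own. This also stands. The stated aim covers touch, not heat. Four touch stimulus types and at least three ROIs (insula, cingulate, orbitofrontal) give 4 × 3 = 12 models at p < 0.05. Precision is low: on the assumed inputs (SD 0.8 per measurement, 24 subjects), requiring both paths to be significant gives about 31% power at a drug-to-BOLD effect of 0.6 and a little over 60% at 1.0.

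**Conclusion.** The concern holds. Section 10a promises a test of whether brain activation mediates the drug effect and then specifies a model that cannot estimate it. This rests on the text alone, together with the reading of stimulus level as the within-modality pairs. The figures are illustrations on assumed inputs and show only that the error can be large and of either sign. The likelier mistake is in the model sentence, not the aim. It should be fixed before the imaging data are analysed. The primary paired t-test, the mood mediation, the drug contrast on activation and the sample size are unaffected.

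**What to change.** Rewrite the model sentence in one of two ways.

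1. **Keep the aim.** Independent variable: drug (naloxone versus saline). Mediator: post-minus-pre ROI parameter estimate. Outcome: the matching post-minus-pre pleasantness rating. Fit it for each touch stimulus type.
2. **Keep stimulus level as independent variable.** Add drug explicitly as moderator, say which paths it moderates, and restate the aim as drug moderation of stimulus-evoked mediation.

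In either case define stimulus level, and do not report a stimulus-level model without drug as mediation of the drug effect. It would also help to state how the several stimulus-by-ROI models will be handled for multiplicity, or to label them exploratory, and to acknowledge the limited precision.

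The cost is wording and minor analysis work. Scans of all sensory conditions before and during infusion in both sessions, and ratings after each block, are already planned in Section 4d. No new data or participants are needed.

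Suggested text for option 1: *For each touch stimulus type and ROI, the independent variable is drug (naloxone or saline), the mediator is the change in ROI activation from pre- to post-infusion, and the dependent variable is the corresponding change in pleasantness rating.*
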